Risks and solutions envisaged for task 2.6: Risk: data loss. Contingency: In order to ensure no data loss, a periodical back up will be carried out.

WP3.- Probiotic effects on AD dementia

The objective of this WP is to enhance the knowledge of the potential positive probiotic effects in the gut composition and on their clinical symptoms of the Alzheimer disease patients. In this sense our group has already done studies of the beneficial effects of the PNU-282987, an alpha 7 nicotinic receptor agonist in an animal model of Alzheimer's disease, with positive results in anxiety symptoms but not in cognitive (Vicens et al, 2013a, 2013b, 2017).

It is generally agreed that probiotic strains should be of host origin with a beneficial effect on the host, withstand into food stuff with a high count of them, withstand transits through intestine and colonize lumen of the tract, produce antimicrobial agents, and be technologically appropriate for industrial production (Shewale et al., 2014). Due to the lack of evidence about the appropriate dosage of probiotics for AD, we used the below-mentioned doses based on few previous studies in healthy subjects (Benton et al., 2007; Mohammadi et al., 2015) and on AD patients with positive results (Akbari et al 2016).

To achieve this objective, the following tasks will be carried out in this WP:

Task 3.1. Patients recruitment and assignment to experimental groups

We will recruit a total of 60 AD patients, 30 will ingest the probiotic mixture and 30 will ingest placebo (randomized assignment to the groups will be done). The experimental group will take the probiotic ingest daily: *Lactobacillus acidophilus*, *Lactobacillus casei*, *Bifidobacterium bifidum*, and *Lactobacillus fermentum* (2×10^9 CFU/g of each). This mixture of bacteria has been showed to have positive results with 12 weeks treatment (Akbari et al, 2016). The duration of the treatment will be 24 weeks, with two posttreatment assessment, at 12 weeks and at 24 weeks.

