To calculate sample size, we used the standard formula suggested for clinical trials by considering type one error(a) of 0.05 and type two error(b) of 0.20 (power = 80%) based on a previous study (Akbari et al, 2016). We used 1.3 as SD and 1.1 as the difference in mean (d) of MMSE as key variable. Accordingly, we needed 25 persons in each group. Assuming 5 dropouts in each group, the final sample size was determined to be 30 persons per group. This sample size is enough to detect differences in cognitive performance due to a probiotic treatment (Akbari et al, 2016).

The criteria for the recruitment will be: Inclusion criteria: AD diagnosed by the neurology service; more than 65 years. Exclusion criteria: Comorbidity with other significant neurology disease, infectious treatment with antibiotics in the previous 6 months prior to providing the stool sample, corticosteroid use, immunosuppressors or immunostimulants treatment, illnesses of the GI tract, large doses of commercial probiotics consumed (greater than or equal to 10^8 cfu per organisms per day).

The hospitals will have publicity of the study and when target patients were attended by the neurologists/neuropsychologist (group research members) will be informed of the study and encourage enrolling. Also, neuropsychologists of the Alzheimer's Association will inform of the study and encourage enrolling. In the Alzheimer stimulation center of Alzheimer Association come regularly about 60-70 patients. If the patients agree to enroll the study, they (or legal tutor) will sign the informed consent and give their contact telephone number to be able to be contacted again. The neurologists/neuropsychologist also will give them the stool collection pack, to be kept for them until the contact of the research team for the interview.

Risks and solutions envisaged for task 3.1: Risk: patient lost from the recruitment until the interview, fail in neuropsychological assessment, fecal collection or treatment adherence. Contingency: we will recruit some more patients of each group 5-10 patients.

Task 3.2. Citation of the volunteers before the probiotic intake period: assessment, stool sample collection and treatment initiation

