Volunteers were contacted and cited for an interview (at the same hospital, center Alzheimer's Association or at home, the more comfortable to them). In order to obtain the stool sample, the researcher will explain the instructions (a paper with the written instructions will be with the kit too) and encourage to collect 1-2 days before the interview and keep in the freeze until they deliver us in the interview (stool collection and preservation system, Norgen, Biotek Corporation, Canada).

At the time of the interview, the volunteer will come accompanied and give the stool sample in the saving tube of the collection kit.

The assessment will include:

-Patient identification, sex, age, level of education, years of schooling, weight and height and diagnostic (others sociodemographic data) and revision of the inclusion/exclusion criteria

-Medication, diseases (diabetes, cholesterol, hypertension, etc)

-Tests/scales:

-Mediterranean lifestyle index interview (MEDLIFE), (Sotos-Prieto, et al, 2015), MEDLIFE will give us information about how the patient follow Mediterranean diet and habits;

-Live Events Questionnaire-Cuestionario de sucesos vitales (CSV), (Sandín & Chorot, 2017), CSV the information about successful stress events that could affect and modify the main relations of the study

-Screening cognitive tests/scales: Mini Mental State Examination (MMSE) (Folstein et al, 1975), Global Deterioration Scale-Functional Assessment Staging (GDS-FAST) (Reisberg, 1982, 1988), Clinical Dementia Rating (CDR) (Hughes, 1982)

-Cognitive Reserve scale (León-Estrada et al, 2017)

-Activities of Daily Living (ADLs) and Neuropsychiatric scale (Test Barcelona-2), (Peña-Casanova, 2019)

-Anxiety and Depression Scale (Goldberg et al 1988)

-Test Barcelona-2 battery, beta abbreviated version (Peña-Casanova, 2019), we will use Test Barcelona-2 battery to an extensive and deep neuropsychology assessment.

The patients were requested not to change their ordinary physical activity and not to take any nutritional supplements during the 12-week trial. The researcher will give to the volunteer in this meeting the treatment to take from the day after the interview until 12 weeks after and a new stool collection kit (in order to bring another stool sample, the next interview day, after 12 weeks).

Task 3.3. Citation of the volunteers after the probiotic intake period: assessment and stool sample collection

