There will be two assessments after 12-week treatment period and 24-week treatment period. At the time of the interview, the volunteer will come accompanied and give the stool sample in the saving tube of the collection kit. The assessment will be the same that in task 3.2.

The researcher will give to the volunteer in the 12-week meeting the treatment to take from the day after the interview until 12 weeks after and a new stool collection kit (in order to bring another stool sample, the next interview day, after 12 weeks).

Task 3.4. Stool samples saving

Same as task 2.4.

Task 3.5. Stool samples shipment to laboratory analysis

Same as task 2.5.

Task 3.6. Obtainment of the data and statistical analysis

The fecal samples will be analyzed by Sequencing Technics and characterize their bacterial taxonomic composition. These data will be received within 2-3 months after the samples reach the analyzer laboratory.

Statistical analysis with microbiota data and all other data collected will be done. All the descriptive for all the data collected will be calculated for each group. Microbiota data from experimental groups and the results of the assessments will be compared (Student's t-test and Pearson Chi-square test). Multivariable logistic regression analyses will be done to relate microbiota composition and results of the neuropsychological assessment.

At the moment of statistical analysis will be ask a methodology specialist to revise them and decide if any other analysis could be interesting to do.

Risks and solutions envisaged for task 3.6: Risk: data loss. Contingency: In order to ensure no data loss, a periodical back-up will be carried out.

WP 4.- Dissemination and formation

This WP aims to effectively disseminate our results in international conferences, publishing the results in international scientific journals of high impact factor (1Q-2Q) and disseminate to the benefit society directly as well as educate of the benefits of the variables studied and resulted positive, e.g. the Mediterranean lifestyle, probiotic consumption etc. To achieve this objective, the following tasks will be carried out in this WP:

Task 4.1. Attendance and presentation of communications to congresses

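### The request to avoid supplements and keep activity unchanged is written for a 12-week trial, but treatment and the last assessment run to week 24

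*Combined protocol and SAP*

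**What the plan says.** The combined protocol and SAP sets the length of the probiotic trial in WP3, Task 3.1: "The duration of the treatment will be 24 weeks, with two posttreatment assessment, at 12 weeks and at 24 weeks". Task 3.3 confirms both visits: "There will be two assessments after 12-week treatment period and 24-week treatment period".

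The request on behaviour during the trial appears once, in Task 3.2, after the list of baseline tests: "The patients were requested not to change their ordinary physical activity and not to take any nutritional supplements during the 12-week trial". The next sentence deals with the first supply: "The researcher will give to the volunteer in this meeting the treatment to take from the day after the interview until 12 weeks after".

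Task 3.3 carries one thing over from the baseline visit, "The assessment will be the same that in task 3.2", and then provides for the second supply: "The researcher will give to the volunteer in the 12-week meeting the treatment to take from the day after the interview", again for 12 weeks, with another stool kit. It does not mention supplements or physical activity.

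**The concern.** The request exists to keep outside influences on the gut and on test performance steady while the probiotic is compared with placebo. That matters here because gut composition is itself an outcome, and supplements can include other probiotics. If the request ends at week 12, a patient who starts a supplement or changes physical activity in weeks 13 to 24 has not departed from anything in the written plan. The week-24 stool sample and cognitive tests would then follow 12 weeks with no stated restriction.

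At stake is the clarity of the week-24 comparison, which is the longer exposure and goes beyond the 12-week result that the plan cites for this mixture. Uncontrolled use in either arm could add variation, and use of outside probiotics by placebo patients could narrow the difference between arms. The week-12 comparison is covered by the request as written.

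**Working it through.** This is a comparison of stated durations. No sample-size or power formula bears on it.

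**Inputs**

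| Item | Value | Place |
|---|---|---|
| Treatment duration | 24 weeks | WP3, Task 3.1 |
| Post-baseline assessments | weeks 12 and 24 | Tasks 3.1 and 3.3 |
| First supply | 12 weeks | Task 3.2 |
| Second supply | 12 weeks | Task 3.3 |
| Period named in the request | 12 weeks | Task 3.2 |

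**Step 1: reproduce the plan's duration.** First supply plus second supply: 12 + 12 = 24 weeks. This agrees with Task 3.1, so 24 weeks is the working duration and the 12 in the request is the figure out of line.

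**Step 2: time outside the request.** 24 − 12 = 12 weeks, and 12/24 = 50% of the treatment period.

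**Step 3: assessments outside the request.** Week 12 falls inside and week 24 falls outside, so 1 of 2.

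**Step 4: is the request renewed elsewhere?** The week-12 meeting in Task 3.3 consists of the assessment, a stool sample, a new supply and a new stool kit. Tasks 3.4 to 3.6 deal with storage, shipment and analysis. None of them repeats or extends the request. What carries over from Task 3.2 is the assessment, and the request stands outside that list.

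**Step 5: try the alternative readings.** If the phrase means the first 12-week treatment period, the request still ends at week 12. If it means the whole trial, the stated number is wrong. The request reaches week 24 only if the reader overrides the number.

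**Step 6: what the repeated assessment adds.** The Task 3.2 list includes a review of the inclusion and exclusion criteria, current medication and the MEDLIFE questionnaire on diet and habits. All are repeated at weeks 12 and 24. One exclusion criterion in Task 3.1 is commercial probiotic intake of at least 10^8 cfu per organism per day, so intake at that level could come to light. Lower doses and other supplements are not clearly covered, and the plan does not say what follows if use is found after baseline.

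**The case against.** The strongest reply is that this is a stale number that nobody would follow. Task 3.1 cites a 12-week result for the same bacteria ("This mixture of bacteria has been showed to have positive results with 12 weeks treatment"), and the figure may have been carried over from there. Staff who run a 24-week trial would take the request to last as long as the trial. The repeated criteria review, medication history and MEDLIFE would in any case bring some outside use to notice.

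Much of this stands. A carried-over figure is the likeliest explanation, although the documents do not establish it, and nothing suggests that anyone chose to restrict supplements for only half the treatment. The repeated assessment is a real partial safeguard, strongest against high-dose probiotics.

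Two things remain. The sentence right after the request hands out treatment for exactly the first 12 weeks, so tying the request to that supply is a natural literal reading. And an assessment records what patients did; it does not ask them to abstain.

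A reader might go further and infer a measurable loss of power at week 24. The documents do not support that. The planning figures ("We used 1.3 as SD and 1.1 as the difference in mean (d) of MMSE as key variable") are attached to no visit, and no rate of supplement use is given. Any power figure would therefore rest wholly on assumed contamination. A reader might also infer bias in favour of one arm. Assignment is randomised with a placebo control and the request is worded the same for everyone, so a directional effect is unlikely.

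**Conclusion.** The point holds as a minor internal inconsistency: an operative instruction that is wrong as written. Taken literally, it leaves 12 of 24 treatment weeks and the week-24 assessment uncovered. The possible consequence is added noise or dilution in the week-24 microbiota and test comparisons, of unknown and possibly nil size. Planned sample size, power and type I error do not change.

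Confidence is high that the durations disagree. It does not extend to any effect on results, which depends on how staff read the sentence and on how many patients would act differently after week 12. A reader might also conclude that patients were in fact told they were free to take supplements after week 12. That cannot be judged, because the consent pages are not in this copy; the point concerns the text of the plan.

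**What to change.** In WP3, Task 3.2, and in any matching patient instruction, replace the reference to a 12-week trial with *during the 24-week treatment period*. In Task 3.3, add one sentence saying that the request is repeated at the week-12 meeting, when the second supply is handed over.

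The cost is one wording amendment and a reminder at a meeting that already takes place. As an optional extra, supplement intake could be asked about directly at the existing week-12 and week-24 interviews; the correction does not depend on it.

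### Task 3.6 compares MMSE between arms with a plain t-test and states no use of the baseline MMSE, although adjusting for it would gain precision at almost no cost

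*Combined protocol and SAP*

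**What the plan says.** Task 3.1 sizes the trial on MMSE: "We used 1.3 as SD and 1.1 as the difference in mean (d) of MMSE as key variable". With a type I error of 0.05 and 80% power it arrives at 25 per group, raised to 30 to allow for 5 dropouts in each.

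The baseline score is already collected. The pre-treatment battery in Task 3.2 includes "Screening cognitive tests/scales: Mini Mental State Examination (MMSE"). Task 3.3 repeats it: "There will be two assessments after 12-week treatment period and 24-week treatment period", and "The assessment will be the same that in task 3.2".

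For the analysis, Task 3.6 states: "Microbiota data from experimental groups and the results of the assessments will be compared (Student's t-test and Pearson Chi-square test"). The one regression it names has another purpose: "Multivariable logistic regression analyses will be done to relate microbiota composition and results of the neuropsychological assessment". It also provides for a methodology specialist to review the analyses when they are done and to consider others. WP3 mentions no baseline covariate, change score or repeated-measures model, and names no visit for the main MMSE comparison.

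**The concern.** A chi-square test does not suit a continuous score, and the logistic regression does not compare arms. That leaves the t-test for MMSE, with two gaps.

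- **Unused information.** Two MMSE scores from the same patient are normally correlated. Entry to WP3 requires an AD diagnosis and an age above 65 but sets no MMSE range, so patients may differ widely at baseline. A t-test on follow-up scores carries all of that spread into the error term. A t-test on change removes part of it but adds the noise of the baseline measurement.
- **Undefined quantity.** Task 3.1 does not say whether 1.3 is the SD of a follow-up score, of a change, or of a baseline-adjusted residual. If the SD belongs to one quantity and the test is run on another, the power differs from the planned 80%.

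With only 25 evaluable patients per arm, either gap could decide whether a real difference of 1.1 points is detected.

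**Working it through.** **Inputs from Task 3.1:** difference 1.1, SD 1.3, alpha 0.05, power 80%, 25 evaluable per group. **Assumed:** two-sided test, equal variances at baseline and follow-up, and a baseline-to-follow-up correlation r, which the documents do not give and which is shown from 0.3 to 0.9.

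**Step 1: the plan's own figure.** The normal formula gives 2 × [1.3 × (1.960 + 0.842) / 1.1]² = 21.9, so 22 per group. The noncentral-t calculation gives 23 (80.1% power). The stated 25 is within two patients of that and has 83.4% power. The largest SD that keeps 80% power with 25 per group is about 1.36. Dropout: 25 / (1 − 5/30) = 30, as stated.

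**Step 2: SD of each analysed quantity.** With s the SD of a follow-up score:

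- t-test on follow-up: s
- t-test on change: s√(2(1 − r))
- ANCOVA: s√(1 − r²)

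The large-sample variance of ANCOVA is therefore (1 − r²) times that of the follow-up t-test. It is (1 − r²)/(2(1 − r)) = (1 + r)/2 times that of the change t-test. Neither ratio exceeds 1.

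**Step 3: small-sample cost.** ANCOVA uses 47 rather than 48 degrees of freedom. Chance baseline imbalance multiplies its variance by about 1 + 1/(2 × 25 − 4) = 1 + 1/46 = 1.022. Both costs are included in the ANCOVA figures below.

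**Step 4: power with 25 per group (%),** for each reading of 1.3:

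| Meaning of 1.3 | r | s | t-test, follow-up | t-test, change | ANCOVA |
|---|---|---|---|---|---|
| A: follow-up SD | 0.3 | 1.300 | 83.4 | 69.8 | 86.0 |
| A | 0.5 | 1.300 | 83.4 | 83.4 | 91.7 |
| A | 0.7 | 1.300 | 83.4 | 96.6 | 98.2 |
| B: SD of change | 0.5 | 1.300 | 83.4 | 83.4 | 91.7 |
| B | 0.7 | 1.678 | 62.2 | 83.4 | 88.2 |
| B | 0.8 | 2.055 | 45.8 | 83.4 | 86.3 |
| B | 0.9 | 2.907 | 25.9 | 83.4 | 84.5 |
| C: residual SD | 0.5 | 1.501 | 71.9 | 71.9 | 82.6 |
| C | 0.7 | 1.820 | 55.3 | 77.1 | 82.6 |
| C | 0.8 | 2.167 | 42.0 | 79.4 | 82.6 |
| C | 0.9 | 2.982 | 24.8 | 81.5 | 82.6 |

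In B, s = 1.3/√(2(1 − r)); in C, s = 1.3/√(1 − r²). Example (B, r = 0.7): s = 1.3/√0.6 = 1.678, and the residual SD is 1.678 × √0.51 = 1.199.

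**Step 5: equivalent sample size, before the small-sample cost.** ANCOVA with 25 per group matches a follow-up t-test with 25/(1 − r²) per group: about 33 at r = 0.5 and 49 at r = 0.7. It matches a change t-test with 25/((1 + r)/2) per group: about 33, 29, 28 and 26 at r = 0.5, 0.7, 0.8 and 0.9.

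**Step 6: where adjustment stops paying.** With 1.3 as the follow-up SD, ANCOVA has 82.6% power at r = 0 against 83.4% for the follow-up t-test, and the two are level near r = 0.15. Against the change t-test with 1.3 as the SD of change, they are level near r = 0.95.

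**Step 7: simulation.** Simulated trials (40,000 per setting) agree: in A, ANCOVA power is 91.8% at r = 0.5 and 98.2% at r = 0.7. In null simulations (100,000 trials; r = 0.5, 0.7, 0.9) all three tests reject in 4.9–5.1% of trials, so all are valid.

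**The case against.** The strongest reply is that nothing is broken. The t-test is valid, and if it is run on the quantity to which 1.3 refers, it has 83.4% power without adjustment. The lowest figures, 25–46%, need two things the documents do not show: that 1.3 is a change or residual SD, and that the t-test is run on raw follow-up scores. The source cited for the 1.3 may define it. This stands: nothing here shows that 1.3 is wrong, and those figures are conditional.

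It is also true that adjustment is not strictly free at this size. Below r of about 0.15, or above about 0.95 against a change score, it loses a little, but under one percentage point. The gain can be modest too: 2.6 points at r = 0.3 under reading A, and about one point against a change t-test at r = 0.9.

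Finally, the specialist review in Task 3.6 leaves room for ANCOVA. But it takes place when the data are analysed and commits the plan to nothing. Deciding on adjustment then is a choice that should be fixed beforehand.

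**Conclusion.** The point holds, as an improvement in efficiency and pre-specification rather than an error that invalidates the trial. Task 3.6 names one usable test for MMSE between arms and gives the baseline score no role. In every row of the table ANCOVA has the highest power. Against the t-test on follow-up scores the gain is 2.6 points (r = 0.3), 8.3 points (r = 0.5) and 14.8 points (r = 0.7) if 1.3 is the follow-up SD. Against the t-test on change it runs from about 1 point at r = 0.9 (readings B and C) to 8–11 points at r = 0.5. Under reading C, adjustment is what delivers roughly the intended power and adds nothing beyond it.

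The size rests on an assumed r, a two-sided test, equal variances and 25 evaluable patients per arm. The direction holds for any correlation between about 0.15 and 0.95, and outside that range the loss is below one point.

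**What to change.** In Task 3.6, replace the t-test for MMSE with: *the arms will be compared by ANCOVA of the follow-up MMSE score, with treatment group as factor and baseline MMSE as covariate*. A mixed model of the week-12 and week-24 scores with baseline as covariate is an acceptable alternative, but one of the two should be named as the main analysis. List the other continuous scales to be analysed in the same way, and keep the chi-square test for categorical data.

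Supporting wording:

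- Name one visit for the main MMSE comparison before outcome data are examined.
- In Task 3.1, say which SD the 1.3 is. With 25 per group, 80% power needs an SD of the analysed quantity of about 1.36 or less. For an ANCOVA residual SD, allowing for chance imbalance, the limit is about 1.34.
- Reconcile the durations, since the choice of visit depends on them. Task 3.1 says "The duration of the treatment will be 24 weeks, with two posttreatment assessment, at 12 weeks and at 24 weeks", while Task 3.2 asks patients "not to take any nutritional supplements during the 12-week trial".

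The cost is protocol and SAP wording and one degree of freedom, plus the small imbalance term above. No new data, visits or patients are needed, because the baseline MMSE is already collected in Task 3.2.

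### WP3 is sized on one MMSE comparison at 5%, but Task 3.6 names no deciding visit, no order of endpoints and no error control

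*Combined protocol and SAP*

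**What the plan says.** **Sizing (WP3, Task 3.1).** The calculation uses alpha 0.05 and power 80%, and continues: "We used 1.3 as SD and 1.1 as the difference in mean (d) of MMSE as key variable". It arrives at 25 per group, raised to 30 for dropout. It names no visit, and does not say whether the SD is that of the score at a visit or of the change from baseline.

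**Visits (Tasks 3.1 to 3.3).** "The duration of the treatment will be 24 weeks, with two posttreatment assessment, at 12 weeks and at 24 weeks". MMSE is collected at baseline (Task 3.2: "Screening cognitive tests/scales: Mini Mental State Examination (MMSE" and other scales), and for both later visits Task 3.3 states "The assessment will be the same that in task 3.2".

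**Analysis (Task 3.6).** "Microbiota data from experimental groups and the results of the assessments will be compared (Student's t-test and Pearson Chi-square test"). Logistic regressions relating microbiota to the neuropsychological results follow. A methodology specialist is then to review the analyses at the time they are done and "decide if any other analysis could be interesting to do". Task 3.6 does not mention MMSE, a primary comparison, a deciding visit, a ranking of endpoints or an adjustment for multiple tests. No other section supplies these.

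**The concern.** The sample size rests on one test at 5%. The analysis section describes a set of tests of equal standing at two visits, and allows more to be added later. A reader of the plan cannot tell which result would make the trial positive or negative. Even with MMSE accepted as the intended main variable, the week-12 or the week-24 comparison could be presented as the trial's result once both are known. That choice cannot be made credibly after the data are seen.

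The second gap concerns power. The t-test in Task 3.6 makes no use of baseline MMSE. Whether it has the planned power depends on what SD 1.3 describes, which Task 3.1 does not say.

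**Working it through.** **Inputs from Task 3.1:** difference 1.1, SD 1.3, alpha 0.05 (taken as two-sided, since sidedness is not stated), power 0.80, 25 evaluable per group. **Assumed, because the documents give none:** the correlation between weeks 12 and 24 (0.5 to 0.9), the correlation between baseline and follow-up (0.3 to 0.9), and equal SDs at baseline and follow-up.

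**1. The plan's own figure.** Standardised difference = 1.1/1.3 = 0.846. Normal formula: n = 2 × [(1.960 + 0.842)/0.846]² = 21.9, so 22 per group. The exact t-test needs 22.9, so 23. The stated 25 is slightly generous. At 25 per group the two-sided t-test has power 0.83. Dropout: 25 + 5 = 30. The sizing is sound for one test.

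**2. MMSE at both visits, each at 0.05, either may count.** Under no effect, the chance of at least one false positive is 1 − P(|Z₁| ≤ 1.96 and |Z₂| ≤ 1.96), with Z₁ and Z₂ bivariate normal.

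| Assumed visit correlation | Chance of a false positive |
|---|---|
| 0.5 | 9.1% |
| 0.7 | 8.3% |
| 0.8 | 7.8% |
| 0.9 | 7.0% |

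Simulated t-tests with 25 per arm agree (9.2%, 8.4%, 7.9%, 6.9%). Independent visits would give 1 − 0.95² = 9.75%.

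**3. What SD 1.3 refers to.** If it is the visit-score SD, the unadjusted t-test has power 0.83. If it is the SD of change, then SD(change) = SD(visit) × √[2(1 − ρ)], so SD(visit) = 1.3/√[2(1 − ρ)], where ρ is the baseline correlation. Power of an unadjusted t-test on visit scores, 25 per group:

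| ρ | SD(visit) | Power |
|---|---|---|
| 0.3 | 1.10 | 0.93 |
| 0.5 | 1.30 | 0.83 |
| 0.7 | 1.68 | 0.62 |
| 0.8 | 2.06 | 0.46 |
| 0.9 | 2.91 | 0.26 |

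**4. Baseline-adjusted comparison.** Residual SD = SD(visit) × √(1 − ρ²), with 47 degrees of freedom and a small allowance for estimating the slope. Example, 1.3 as change SD and ρ = 0.9: 2.907 × √0.19 = 1.267; 1.1/1.267 = 0.868; power 0.845.

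| ρ | Power, 1.3 as visit SD | Power, 1.3 as change SD |
|---|---|---|
| 0.3 | 0.86 | 0.95 |
| 0.5 | 0.92 | 0.92 |
| 0.7 | 0.98 | 0.88 |
| 0.9 | >0.99 | 0.845 |

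The lowest value is 0.845, so adjustment keeps the planned power under either reading of the SD.

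**5. Alternative: alpha split, 0.025 per visit.** For unadjusted tests with 1.3 as visit SD, power is 0.75 at each visit. Power to succeed at one or both is 0.88, 0.85, 0.83 or 0.81 at visit correlation 0.5, 0.7, 0.8 or 0.9, if the effect is the same at both visits.

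**The case against.** The best reply is that the plan already ranks MMSE first: Task 3.1 singles it out and sizes on it alone. That stands, and a reader who inferred that the trial has no identifiable main variable would go too far. It does not settle the visit. One might infer week 12, because Task 3.1 draws its inputs from an earlier study that it links to 12 weeks of treatment. The plan does not say so, and treatment runs to 24 weeks.

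It can also be said that WP3 is framed modestly, to "enhance the knowledge of the potential positive probiotic effects in the gut composition and on their clinical symptoms", and that nowhere does the plan declare success on either visit. The second part is correct, so the 7.0-9.1% is conditional on either visit being allowed to count. The plan does not exclude that use.

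The natural reading of Tasks 3.1 and 3.6 is a comparison of visit scores, since change from baseline is not mentioned. This limits two tempting inferences:

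- Testing both value and change at both visits would give about 15-16%, but the plan describes no change-score test.
- The 0.62 in step 3 might be read as showing an underpowered trial. It is one point in a range of 0.26 to 0.93, and it applies only if 1.3 is the SD of change.

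A reader might also infer that a significant result on any scale counts as success, which gives much larger error rates. Those depend on an assumed number of scores and on a success rule that the plan does not state. Nor does the plan say that taxa are tested one by one, so no taxon error rate can be given.

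**Conclusion.** The concern holds in this form: the test that Task 3.1 sizes is not carried into Task 3.6 as a defined primary comparison. The missing visit, ranking and error control can be confirmed on the page and rest on no assumption. The size on MMSE alone is a false-positive chance of 7.0-9.1% against the 5% used for sizing, given separate tests at 0.05, either visit counting, and a visit correlation of 0.9 to 0.5. This inflation is moderate, but the correction has to precede sight of the data.

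The meaning of SD 1.3 is a real ambiguity with an uncertain consequence. Power of the stated t-test is 0.83 if it is the visit-score SD, and between 0.26 and 0.93 if it is the SD of change, for baseline correlation 0.9 to 0.3. The documents do not show that the trial is underpowered.

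**What to change.** In Task 3.6, before data are seen:

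1. Name one primary comparison: MMSE at one stated visit, between arms, two-sided 0.05, adjusted for the baseline MMSE that Task 3.2 already collects.
2. Test MMSE at the other visit, in the same form, only if the first is significant. A pre-stated split of alpha over the two visits is an acceptable alternative.
3. Label all other scores, the microbiota comparisons and any analysis added later as exploratory.
4. In Task 3.1, state whether SD 1.3 and difference 1.1 refer to the visit score or to change.

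Separately, Task 3.2 describes the trial as lasting 12 weeks while Task 3.1 gives 24 weeks of treatment. These passages must be reconciled.

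**Cost.** Wording only, with no extra patients or assessments. An MMSE effect present only at the non-primary visit would not count as the primary result, and the remaining results carry less weight. The sponsor chooses the visit.
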